3.2 Sample Size

Subjects will be randomized as follows:

- Cohort 1: ~36 subjects in 2:1 randomization ratio (~24 subjects to etrasimod 2 mg and ~12 subjects to placebo)
- Cohort 2: ~42 subjects with SALT I < 95 at Baseline in 4:1:2 randomization ratio (~24 subjects to etrasimod 3 mg, ~6 subjects to etrasimod 2 mg, and ~12 subjects to placebo)

Assuming a 15% drop-out rate from the study over 24 weeks, at least 35 treatment completers (20 subjects to etrasimod 3 mg, 5 subjects to etrasimod 2 mg, and 10 subjects to placebo from Cohort 2; plus subjects from Cohort 1 with SALT I < 95 at Baseline) at Week 24 will provide at least 80% and 47% power to detect a treatment difference of 20% for etrasimod 3 mg and etrasimod 2 mg from placebo, respectively, in the percent change from Baseline in SALT I at Week 24 by a 2-sample t-test using a 2-sided significance test level of 0.05 and common standard deviation (SD) of 17.8%.

3.3 Treatment Randomization and Unblinding Procedures

Under protocol amendments 1.0 and 1.1 (Cohort 1), randomization will take place at the Day 1 visit prior to first dosing. Subjects who complete all Screening requirements and remain eligible for the study will be randomized in a 2:1 ratio to receive etrasimod 2 mg or placebo orally once daily for 24 weeks in the DB Treatment Period. The randomization will be stratified by SALT I score (< 100, 100) at Day 1/Baseline.

Subjects enrolled during Amendment 2.0 and later (Cohort 2) who complete all Screening requirements and remain eligible for the study will be randomized in a 4:1:2 ratio to receive etrasimod 3 mg, etrasimod 2 mg, or placebo orally once daily for 24 weeks in the Double-Blind Treatment Period.

This study includes a DB Treatment Period with limited access to the randomization code. The Unblinding Plan documents the procedure for unblinding.

After completing the 24-week DB Treatment Period, eligibility for participation in the OLE Period will be determined. All eligible subjects in Cohort 1 will receive etrasimod 2 mg orally, for at least 1 week during the OLE Period. Subjects in Cohort 1 will transition to 3 mg at the Week 25 visit or at their next OLE study visit after the implementation of Amendments 2.0 and 2.1. Subjects in Cohort 2 will receive etrasimod 2 mg orally, once daily for 1 week during the OLE Period and then transition to etrasimod 3 mg orally, once daily for the remainder of the OLE Period. Subjects from Cohort 1 who are already in the OLE Period at the time of Amendments 2.0 and 2.1 implementation may be allowed to continue on etrasimod 2 mg at the Investigator's discretion provided that they have achieved a SALT I score ≤ 20 .

3.4 Schedule of Events

For the statistical analysis, DB Treatment Period will include 24 weeks treatment; OLE Period will include 28 weeks treatment and 4 weeks SFU. The date at which the subject is randomized will be referred to as the “Day 1/Baseline”. Subjects will be requested to attend the following scheduled visits for the DB Treatment Period from their Day 1/Baseline visit: Weeks 1, 2, 4, 8, 12, 16, 20, 24 visits as applicable (Week 1 visit is applicable to Cohort 2 only). For the OLE Period, subjects will attend scheduled visits at Week 24 (this will be same as Week 24 in the DB Treatment Period), and Weeks 25, 28, 36, 44, and 52. Subjects who terminate the study drug early in the DB Treatment Period or OLE Period should have SFU Visits 2 weeks and 4 weeks after the last dose of study drug. Visits subjects make to the clinic outside the visit window are recorded as unscheduled visits. Refer to Schedules of Assessments (Appendix 1 and Appendix 2 in the protocol) for more details.

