9.4. Follow-Up/End of Study

Subjects who complete the Open-Label Extension Period will return for Safety Follow-Up Visits 2 weeks (± 3 days) and 4 weeks (± 3 days) after the last dose of study drug (which corresponds

to Week 54 and Week 56, respectively). Visit assessments are detailed in the Schedules of Assessments ([Appendix 1](#) and [Appendix 2](#)).

Subjects who terminate the study drug early in the Double-Blind Treatment Period or Open-Label Extension Period should have Safety Follow-Up Visits 2 weeks (± 3 days) and 4 weeks (± 3 days) after the last dose of study drug.

The final Safety Follow-Up Visit (ie, SFU 2) will also be the End of Study Visit.

All AEs should be recorded for up to 30 days after last dose of study drug (Section [10.5.8.2.2](#)).

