4.3 Windowing Conventions

When available, visits will be analyzed as scheduled (refer to protocol Appendices 1 and 2). ET and/or unscheduled/retest measurements will only be included if a scheduled measurement is not available, and the ET or unscheduled/retest measurement falls within the analysis visit windows as described in [Table 1](#).

If there is more than one retest, unscheduled or ET assessment for a given analysis visit, the assessment closest to the target day will be retained for data summary of that visit; if there are 2

observations with equal distance to the target day, then the later one will be retained. All data from scheduled, retest, unscheduled, and ET visit assessments will be listed.

Table 1: Analysis Visit Windows

Analysis Visit	Target Study Day	Visit Window (Period Day)
DB Treatment Period		
DB Baseline	1	Refer to DB Treatment Period Baseline definition in Section 4.1
Week 1 (Cohort 2 only)	Day 8	Post first dose – Day 11
Week 2	Day 15	Cohort 1: Post first dose – Day 21 Cohort 2: Day 12 – Day 21
Week 4	Day 29	Day 22 – Day 42
Week 8	Day 57	Day 43 – Day 70
Week 12	Day 85	Day 71 – Day 98
Week 16	Day 113	Day 99 – Day 126
Week 20	Day 141	Day 127– Day 154
Week 24*	Day 169	Day 155 – (Last treatment day + 6) in DB period for subjects never treated in OLE; Day 155 – Pre first dose in OLE for subjects treated in OLE
OLE Period **		
OLE Baseline	OLE Day 1	Refer to OLE Period Baseline definition in Section 4.1
Week 25	OLE Day 8	Post first dose in OLE – OLE Day 18
Week 28	OLE Day 29	OLE Day 19 – OLE Day 56
Week 36	OLE Day 85	OLE Day 57 – OLE Day 112
Week 44	OLE Day 141	OLE Day 113 – OLE Day 168
Week 52	OLE Day 197	OLE Day 169 – (Last treatment day + 6)
Safety Follow-up 1	Last treatment day + 14 days (± 3 days)	(Last treatment day + 7) – (Last treatment day + 21 days)
Safety Follow-up 2	Last treatment day + 28 days (± 3 days)	(Last treatment day + 22 days) - (Last contact day)

DB = Double-Blind; OLE = Open-Label Extension; SFU = Safety Follow-Up

* Week 24 is the last scheduled visit in DB Treatment Period and first scheduled visit in OLE Period.

** The days are Period Day (refer to Section 4.2) in the OLE Period.

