OLE Safety Set (OLE SAF)	
The OLE SAF includes all subjects who received at least one dose of study drug in the OLE Period.
 
All safety analysis in the OLE Period will be performed using OLE SAF. All subjects will be analyzed according to the actual treatment they received. In case a subject received more than one actual treatment, the first treatment received will be used for the safety analysis.

OLE Full Analysis Set (OLE FAS)	
The OLE FAS includes all subjects with a SALT I < 95 at Baseline who received at least one dose of study drug in the OLE Period.
 
All efficacy analysis in the OLE Period will be performed using OLE FAS. All subjects will be analyzed according to the actual treatment they received. In case a subject received more than one actual treatments, the first treatment received will be used.

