11 SAFETY ANALYSIS

Unless otherwise indicated, safety data will be summarized overall and by treatment group and visit, when applicable, for each study period separately, based on the SAF for the DB Treatment Period and OLE SAF for the OLE Period.

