11.2 Clinical Laboratory

For quantitative laboratory test, descriptive statistics will be presented for data related to chemistry, hematology (including coagulation) and quantitative urinalysis. Observed values and change from baseline values will be presented for each post-baseline visit. Frequencies and percentages of subjects in each result category will be provided for qualitative urinalysis data.

Shift tables from baseline to each post-baseline visits describing shifts to abnormality (low or high) will be provided as well. Only subjects with a baseline result and a result at the specified visit for the parameter will be considered.

Separate listings of all data for chemistry, hematology (including coagulation), urinalysis and pregnancy test will be provided.

In addition, separate listings of data for chemistry, hematology (including coagulation), and urinalysis will be provided for each parameter where a subject had at least one abnormal result.

Incidence of hepatic enzyme elevations will be summarized by visit. The following hepatic enzyme elevations will be reported:

- ALT > 1, >2, > 3, > 5, > 8, > 10, and > 20 x upper limit of normal (ULN)
- AST > 1, > 2, > 3, > 5, > 8, > 10, and > 20 x ULN
- ALT or AST > 3, > 5, > 10, and > 20 x ULN
- ALP > 1, > 1.5, > 2, > 3, > 5, > 8, > 10, and > 20 x ULN
- GGT > 1, > 2, > 3, > 5, > 8, > 10, and > 20 x ULN
- Total bilirubin >1, > 1.5, >2, and >3 x ULN
- ALT or AST > 3 x ULN AND total bilirubin > 1.5 x ULN
- ALT or AST > 3 x ULN AND total bilirubin > 2 x ULN
- ALT or AST > 3 x ULN AND ALP > 1.5 x ULN
- Symptomatic elevation in ALT or AST, defined as an ALT or AST elevation > 3 x ULN in temporal association with nausea, vomiting, anorexia, abdominal pain, or fatigue, where temporal association is defined as onset of symptoms within +/- 14 days of the elevation.

Incidence of absolute lymphocyte count decrease at any time during a study period (post-dose on Day 1 to pre-dose on Week 24 for the DB Treatment Period and post-dose on Week 24 to the 2nd SFU visit for the OLE Period) will be summarized. The following categories will be presented:

- Grade 1, defined as an absolute lymphocyte count ≥ 0.8 to $< 1.02 \times 10^9/L$
- Grade 2, defined as an absolute lymphocyte count ≥ 0.5 to $< 0.8 \times 10^9/L$
- Grade 3, defined as an absolute lymphocyte count ≥ 0.2 to $< 0.5 \times 10^9/L$

- Grade 4, defined as an absolute lymphocyte count ≥ 0.0 to $< 0.2 \times 10^9/L$
- Any Grade 3 or 4
- Any Grade 1 to 4

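### Safety follow-up visits belong to the OLE Period in the SAP, so the follow-up laboratory and vital-sign values of subjects never dosed in the OLE have no by-visit summary

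*SAP*

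**What the plan says.** **Period.** SAP 3.4 defines the periods for analysis: the DB Period is the 24 weeks of treatment, and the "OLE Period will include 28 weeks treatment and 4 weeks SFU". In SAP Table 1 (section 4.3) the SFU 1 and SFU 2 rows stand under the OLE heading. The last DB row, Week 24, runs "Day 155 – (Last treatment day + 6) in DB period for subjects never treated in OLE".

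**Who attends.** SAP 3.4 says "Subjects who terminate the study drug early in the DB Treatment Period or OLE Period should have SFU Visits" at 2 and 4 weeks after the last dose. Protocol 9.4 has the same rule: "Subjects who terminate the study drug early in the Double-Blind Treatment Period or Open-Label Extension Period should have Safety Follow-Up Visits 2 weeks", with a second such visit at 4 weeks. In both schedules of assessments (Protocol Appendices 1 and 2), SFU 1 has hematology and vital signs, and SFU 2 has the full laboratory tests and vital signs.

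**Analysis sets.** Under SAP 11, safety data are summarised by period, "based on the SAF for the DB Treatment Period and OLE SAF for the OLE Period". SAP Table 2 says: "The OLE SAF includes all subjects who received at least one dose of study drug in the OLE Period". SAP 11.8 names a different set for OLE safety, the OLE FAS, which also requires an OLE dose.

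**Lymphocyte grades.** SAP 11.2 tabulates decreases at any time in a period. The DB interval runs from after the Day 1 dose to before the Week 24 dose. The OLE interval runs "post-dose on Week 24 to the 2nd SFU visit for the OLE Period".

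**The concern.** The SFU visits are the scheduled off-drug safety check. Under the period rule they are OLE data, and under the analysis-set rule a subject with no OLE dose is not in any OLE table. Taken together, the two rules leave these subjects' SFU values without a by-visit summary, although the visits are required and the data are collected.

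The omission is selective. Those left out include subjects who stopped for safety reasons (Protocol 8.1) and DB completers refused entry to the OLE because of heart rate, blood pressure or ECG findings at Week 24 (Protocol 4.3). Safety in the DB period is part of the primary objective (Protocol 2). Protocol 1.2 describes the lymphocyte reduction as reversible, and Protocol 9.5 asks sites to follow counts after stopping. By-visit summaries of SFU would come only from subjects dosed with etrasimod in the OLE.

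**Working it through.** The plan states no figure on this point. The check traces one group of values through the rules, then bounds the size.

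**1. Can the SFU value enter a DB by-visit table?**
- SAP 4.3 analyses scheduled visits as scheduled. Only ET, unscheduled and retest values are moved by window. SFU 1 and SFU 2 are scheduled visits with their own rows.
- For a subject never treated in the OLE, the Week 24 row closes at last treatment day + 6 and the SFU 1 row opens at + 7.
- The DB laboratory and vital-sign endpoints in SAP 2.2.1.4 end at Week 24.
- No stated rule brings the value in.

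**2. Can it enter an OLE table?** No. Both the OLE SAF (SAP 11) and the OLE FAS (SAP 11.8) require an OLE dose.

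**3. Is there a third table?** SAP Appendix 3 has chemistry, hematology, urinalysis, shift, hepatic, lymphocyte-grade and by-visit vital-sign tables in DB and OLE versions only. Disposition, exposure, concomitant medications and adverse events do have full-study versions. The full-study vital-sign and ECG tables cover cardiac monitoring, which SAP 11.3 and 11.5 define at Day 1 and Week 24.

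**4. What is not lost?**
- Adverse events with onset before any OLE dose are assigned to DB (SAP 11.1).
- ET values can be windowed into DB visits (SAP 4.3).
- Scheduled DB visits attended after stopping, which Protocol 8.1 encourages, are analysed as scheduled.
- Laboratory and vital-sign values are listed on the Safety Set (SAP Appendix 3).

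**5. Lymphocyte table.** The DB interval is not cut at the last dose. Let L be the day of the last dose, and read Week 24 as its target, Day 169 (SAP Table 1). SFU 1 falls at L + 14 and SFU 2 at L + 28, each with a window of 3 days either way, ignored here.

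| Last dose | SFU before Day 169 |
|---|---|
| L ≤ 140 (L + 28 ≤ 168) | SFU 1 and SFU 2 |
| 141 to 154 (L + 14 ≤ 168, L + 28 ≥ 169) | SFU 1 only |
| L ≥ 155 (L + 14 ≥ 169) | neither |

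On that reading, both SFU counts of a subject who stops by Day 140 are already in the table. The SAP does not say that this is the reading: the interval ends before a Week 24 dose that such a subject never takes. A DB completer with a last dose on Day 168 has SFU at Days 182 and 196, after Day 169.

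**6. Size.** Planned N is 36 + 42 = 78, and the assumed study drop-out over 24 weeks is 15% (Protocol 11.2, SAP 3.2).
- 0.15 × 78 = 11.7, about 12.
- Etrasimod: 24 + 6 + 24 = 54, and 0.15 × 54 = 8.1. Placebo: 12 + 12 = 24, and 0.15 × 24 = 3.6.
- Assumed range: 0.05 × 78 = 3.9 and 0.25 × 78 = 19.5, so about 4 to 20.

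These figures show scale and are not an estimate. The 15% counts study drop-outs. Protocol 8.2 ends all evaluation when consent is withdrawn, so some drop-outs have no SFU data. DB completers who do not enter the OLE would add to the count. Protocol 9.4 does not name them, but they stop drug before Week 52, and I have taken them to have SFU.

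**The case against.** The strongest objection is that this is a matter of presentation. Recovery after stopping is neither an objective nor an endpoint. Even the OLE laboratory endpoints in SAP 2.2.2.2 name Weeks 25 to 52 and not SFU. With so few subjects, listings are a reasonable vehicle. The table layouts are in a separate document (SAP 4), and SAP 11.2 promises values at each post-baseline visit, so the DB tables might carry SFU rows.

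Much of this stands and keeps the point minor. It does not remove it. The SAP contains a rule that puts SFU in the OLE and none that would put SFU rows in a DB table. SFU also counts in the OLE lymphocyte table, so the SAP does mean to summarise some SFU data.

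A reader might infer more than the documents support:
- **That all post-drug laboratory and vital-sign data of DB stoppers are unsummarised.** ET visits and scheduled visits attended after stopping reach the DB tables.
- **That SAP 11.2 shuts SFU counts out of the lymphocyte table.** On a calendar reading, most early stoppers' counts are inside its DB interval. The defect is the undefined end point.
- **That about 12 subjects are missing from every summary.** The 15% is study drop-out, and these subjects' on-treatment, ET and adverse event data are summarised.
- **That a placebo-controlled view of recovery is being lost.** At 15% it would be roughly 4 placebo subjects against 8 on etrasimod split over two doses, selected by stopping at different times. That is not a randomised comparison.

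**Conclusion.** The gap holds in limited form. For subjects never dosed in the OLE, the SFU hematology (SFU 1), full laboratory tests (SFU 2), and the hepatic, shift and vital-sign values that go with them have no by-visit summary and appear only in Safety Set listings. This follows from stated rules and not merely from missing detail. The end of the DB lymphocyte interval is undefined for a subject with no Week 24 dose, so two programmers could produce different tables.

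The severity is minor, and no efficacy result is touched. The number affected is unknown: about 12 of 78 if the planned drop-out rate is taken as a rough guide, or about 4 to 20 at an assumed 5% to 25%. The conclusion rests on the SAP text and its table list, because the table layouts are not available. It is worth correcting because the subjects left out are the early stoppers and those refused the OLE, and the data are already being collected.

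**What to change.** Four changes to the SAP:

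- **Sections 3.4 and Table 1:** assign SFU 1 and SFU 2 to the period of the subject's last dose.
- **DB Safety Set tables:** add SFU 1 and SFU 2 rows to the laboratory, hepatic, shift and vital-sign tables for subjects never dosed in the OLE. Present them by actual DB treatment, which is the Safety Set rule in SAP Table 2. ECG rows are not proposed: as the schedules read, Cohort 1 has an SFU 2 ECG and Cohort 2 has no SFU ECG.
- **Section 11.2:** end the DB lymphocyte interval at SFU 2 for subjects never dosed in the OLE.
- **Sections 11 and 11.8:** reconcile the OLE SAF with the OLE FAS. The OLE FAS also drops subjects with Baseline SALT I of 95 or more, while SAP Table 4 and the Appendix 3 titles keep OLE safety on the OLE Safety Set.

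The cost is a few sentences and some extra rows in existing tables, with no new data. The rows will hold small numbers, should be read descriptively, and will not give a reliable contrast with placebo.

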4 GENERAL CONSIDERATIONS

Formats and layouts of TLF will be provided in a separate document (output general layout is described in Appendix 3).

An analysis of efficacy and safety data will be performed after all subjects have completed or early terminated from the 24-week DB Treatment Period. A final analysis of efficacy and safety data will be performed once all subjects completed or early terminated from the study.

4.1 Baseline

Baseline will be defined separately for DB Treatment Period and OLE Period as follows:

Double-Blind Treatment Period

The Study Baseline or DB Treatment Period Baseline (DB Baseline) will be defined as the last non-missing assessment prior to the first study treatment dose (including unscheduled assessments). If the last non-missing assessment is performed on the same date as the first study treatment and time is not available, the assessment will be considered as baseline, except for adverse events and medications starting on the first study treatment dose date which will be considered post-baseline.

Open-Label Extension Period

The OLE Period Baseline (OLE Baseline) will be defined as the last non-missing assessment prior to the first etrasimod dose started at Week 24 for subjects who received placebo during the DB Treatment Period. For subjects who were on etrasimod in the DB Treatment Period, the OLE Baseline will be taken from the DB Baseline.

Change from Baseline will be defined for both DB Treatment Period and OLE Period as the post-Baseline value minus the Baseline value unless otherwise specified. Percent change from Baseline will be calculated as follows:

Percent change from Baseline (%) = (Change from Baseline / Baseline) x 100.

Percent change from Baseline will be missing in situation where Baseline value equals to 0.

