Number of Subjects (Planned):

A total of approximately 78 subjects are planned to be enrolled in this study. It is estimated that approximately 36 subjects will be enrolled in Cohort 1, including 24 subjects in the etrasimod 2 mg group and 12 subjects in the placebo group. Approximately 42 subjects are planned to be enrolled in Cohort 2, including 24 subjects in the etrasimod 3 mg group, 6 subjects in the etrasimod 2 mg group, and 12 subjects in the placebo group.

Eligibility Criteria:

Inclusion Criteria:

Subjects must meet ALL of the following inclusion criteria to be eligible for enrollment into the study:

Key inclusion criteria

1. Men or women between ≥ 18 and ≤ 70 years of age at the time of informed consent
2. Moderate-to-severe AA as assessed by a SALT I score ≥ 25 and < 95 at Screening and Day 1/Baseline. Severity will also be confirmed by central review of photographs taken during Screening
3. Current episode of hair loss for ≥ 6 months but < 5 years
4. Stable disease condition (no significant growth of hair) in the last 6 months as assessed by the Investigator
5. Willing to keep the same hair style and color (eg, hair products, process, and timing for hair appointments) for the duration of the study

General inclusion criteria

6. Willing and able to comply with all clinic visits and study-related procedures and understand and complete study-related questionnaires
7. Provide signed informed consent prior to conducting any procedures
8. Females must meet either a or b of the following criteria and males must meet criterion c to qualify for the study:
 - a. Female who is not of childbearing potential by one of the following:
 - Postmenopausal, defined as no menses for 12 months without an alternative medical cause
 - Permanent sterilization procedure, such as hysterectomy, bilateral salpingectomy, or bilateral oophorectomy
 - b. Nonpregnant female of childbearing potential and agrees to using a highly effective contraception method during treatment and for 30 days following treatment that can achieve a failure rate of less than 1% per year when used consistently and correctly. The following are considered highly effective birth control methods:
 - Combined (estrogen and progestogen containing) hormonal contraception associated with inhibition of ovulation, which may be oral, intravaginal, or transdermal
 - Progestogen-only hormonal contraception associated with inhibition of ovulation, which may be oral, injected, or implanted

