11.10. Statistical Considerations for the Open-Label Extension Period

The objectives of the Open-Label Extension Period are to evaluate long-term safety and efficacy up to 52 weeks.

All safety outcomes will be analyzed using the Safety Set in the Open-Label Extension, which includes all subjects who received at least 1 dose of etrasimod in the Open-Label Extension Period.

Baseline for the Open-Label Extension Period is defined as the last measurement prior to the first etrasimod dose started at Week 24.

Safety analyses will follow general considerations in Section 11.9.2 to Section 11.9.7 with the following exceptions:

- One treatment group in the Open-Label Extension Period and 3 treatment subgroups in the Double-Blind Treatment Period will be analyzed
- Change from Baseline will be analyzed using change from Double-Blind Treatment Period Baseline and change from Open-Label Extension Period Baseline

Only descriptive statistics will be presented for all efficacy assessments during the Open-Label Extension Period. Dichotomous response outcomes derived from specific scores will be assessed. Continuous variables will be summarized by visit using the number of observations, mean, SD, median, minimum, and maximum; and categorical variables will be summarized by visit using frequency counts and percentages.

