3 STUDY DESIGN

3.1 Design Overview

This is a Phase 2, multicenter, randomized, double-blind, placebo-controlled study to assess the safety and efficacy of etrasimod 2 mg and 3 mg, once daily for up to 52 weeks in subjects with moderate-to-severe AA. The study includes multiple periods: a \leq 4-week Screening Period (to determine subject eligibility), a 24-week DB Treatment Period, a 28-week OLE Period, and a 4-week Safety Follow-Up (SFU) Period for a maximum total study duration of 60 weeks.

This study will include approximately 78 subjects (36 in Cohort 1 and 42 in Cohort 2 as described below) with moderate-to-severe AA with current episode of hair loss for \geq 6 months but $<$ 8 years in Cohort 1 and hair loss for \geq 6 months and $<$ 5 years in Cohort 2 (current episode must also be relatively stable during the last 6 months with no significant regrowth).

[figure not shown]
Subjects will be separated into 2 cohorts as follows:

Cohort 1: All subjects (approximately 36 subjects) enrolled under the original protocol, and Amendments 0.1, 0.2, 1.0, and 1.1.

Subjects will be randomized in a 2:1 ratio to receive etrasimod 2 mg or placebo orally, once daily. Randomization is stratified by SALT I score (< 100 , 100) at Day 1/Baseline. Subjects will complete the DB Treatment Period per their original randomization assignment. Subjects who have entered the OLE Period prior to Amendments 2.0 and 2.1 implementation will transition to 3 mg once daily at their next study visit. Subjects who have not entered the OLE Period prior to Amendments 2.0 and 2.1 implementation will receive etrasimod 2 mg from the Week 24 visit to the Week 25 visit and will transition at the Week 25 visit to etrasimod 3 mg orally, once daily for the remainder of the OLE Period. Of note, subjects already in the OLE Period at the time of Amendments 2.0 and 2.1 implementation may be allowed to continue on etrasimod 2 mg at the Investigator's discretion provided that they have achieved a SALT I score ≤ 20 .

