10.5 Exploratory Efficacy Endpoints during the Open-Label Extension Period

The following efficacy endpoints will be assessed at scheduled visits during the OLE Period up to 52 weeks:

- Change and percent change from Baseline in SALT I over time
- Change from Baseline in AASIS over time
- Change from Baseline in AA-QLI over time
- Change from Baseline in peripheral lymphocyte counts over time
- Proportion of subjects achieving a $\geq 30\%$ improvement from Baseline in SALT I over time
- Proportion of subjects achieving a $\geq 50\%$ improvement from Baseline in SALT I over time
- Proportion of subjects achieving a $\geq 75\%$ improvement from Baseline in SALT I over time
- Proportion of subjects achieving a $\geq 90\%$ improvement from Baseline in SALT I over time
- Proportion of subjects achieving a SALT I score ≤ 10 over time
- Proportion of subjects achieving a SALT I score ≤ 20 over time

These endpoints will be summarized by visit using descriptive statistics based on the OLE FAS, with following considerations:

- Missing data will not be imputed

- Summaries will be provided for the three treatment groups in the OLE Period (OLE 2mg, OLE 2mg/3mg, OLE 3mg) and three randomized treatment groups in the DB Treatment Period (DB 2mg, DB 3mg, DB placebo)
- Change and percent change from baseline in continuous variables will be summarized using change from OLE Baseline and DB Baseline (refer to Section 4.1).

The photographic assessments of the full scalp for all subjects, of the eyebrows and eyelashes for subjects who have hair loss in these areas at Day 1/Baseline, and of the fingernails for subjects with fingernail changes related to AA (eg, pitting, white spots, and roughness) at Day 1/Baseline, will be reported in listing.

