11.8 Safety Analyses during the Open-Label Extension Period

Safety analyses will follow general considerations in previous sections 11.1 to section 11.7 with the following exceptions:

- Summaries will be provided by visit based on the OLE FAS overall, for the three treatment groups in the OLE period (OLE 2mg, OLE 2mg/3mg, OLE 3mg), and the three

randomized treatment groups in the DB Treatment Period (DB 2mg, DB 3mg, DB placebo).

- Change from Baseline will be summarized using change from OLE Baseline and DB Baseline (refer to Section 4.1).

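### SAP 4.1 gives former etrasimod subjects their Day 1 value as OLE Baseline, so change from OLE Baseline duplicates change from DB Baseline for them and mixes time origins in the OLE dose-path and Total columns

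*SAP*

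**What the plan says.** Protocol 11.10 has one rule for all subjects: "Baseline for the Open-Label Extension Period is defined as the last measurement prior to the first etrasimod dose started at Week 24". In the same section, among the exceptions listed for the safety analyses, it asks for change from both the double-blind and the OLE baseline. OLE efficacy is promised only as descriptive statistics.

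SAP 4.1 keeps the Week 24 value for former placebo subjects only. For the rest: "For subjects who were on etrasimod in the DB Treatment Period, the OLE Baseline will be taken from the DB Baseline". SAP Table 4 sets out the protocol rule and its replacement and gives clarification as the reason.

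The SAP then uses both baselines throughout the OLE. For efficacy (10.5): "Change and percent change from baseline in continuous variables will be summarized using change from OLE Baseline and DB Baseline". For safety (11.8): "Change from Baseline will be summarized using change from OLE Baseline and DB Baseline". Both sections report by three OLE dose paths and by three double-blind arms. SAP Appendix 1 adds a Total column and defines the dose-path columns by cohort and dosing history, not by double-blind arm. The OLE 3 mg column, for example, takes in Cohort 2 subjects from placebo, 2 mg and 3 mg.

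**The concern.** Reporting from two baselines is useful only if they differ. For former etrasimod subjects they no longer do, so one of the two summaries carries no information. The paired change from Week 24 onward is missing for them. It is the most direct view of what follows the switch from 2 mg to 3 mg (30 planned double-blind 2 mg subjects, with some permitted exceptions in Cohort 1) or the return to 3 mg after one week at 2 mg (24 planned 3 mg subjects). Protocol 3.2 says the extension is meant to assess 3 mg as long-term therapy.

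The second problem is interpretation. A mean that combines change since Week 24 in some subjects with change since Day 1 in others describes neither period. A reader of a column headed change from OLE Baseline would take it as change during the extension, although part of it accrued before the extension began.

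**Working it through.** **Inputs.** Total: "A total of approximately 78 subjects are planned to be enrolled in this study" (Protocol synopsis). Cohort 1 arms: "including 24 subjects in the etrasimod 2 mg group and 12 subjects in the placebo group". Cohort 2 arms: "including 24 subjects in the etrasimod 3 mg group, 6 subjects in the etrasimod 2 mg group, and 12 subjects in the placebo group". Periods: "a 24-week DB Treatment Period, a 28-week OLE Period" (SAP 3.1).

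**The plan's own figures.** 36 subjects at 2:1 give 24 and 12. 42 subjects at 4:1:2 give 24, 6 and 12. 36 + 42 = 78. The stated arm sizes are reproduced.

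**Share with identical baselines.** Etrasimod in the double-blind period: 24 + 6 + 24 = 54. Placebo: 12 + 12 = 24. 54/78 = 69.2%.

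This is a share of planned randomized subjects. The documents do not give the size of the OLE sets, so the range below rests on assumptions:

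- Equal 15% dropout (the SAP 3.2 rate, applied to all arms): 45.9/(45.9 + 20.4) = 69.2%.
- Dropout of 25% on etrasimod and 5% on placebo (assumed): 40.5/(40.5 + 22.8) = 64.0%.
- Dropout of 5% on etrasimod and 25% on placebo (assumed): 51.3/(51.3 + 18.0) = 74.0%.
- SALT I < 95 restriction, with c Cohort 1 subjects kept at 2:1: (30 + 2c/3)/(42 + c). This is 69.2% at c = 36 and 71.4% at c = 0.

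**Weeks covered by change from OLE Baseline.** At nominal visit week w, this is w − 24 for former placebo and w for former etrasimod. The Total column at the planned mix averages [54w + 24(w − 24)]/78.

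| Visit | Former placebo | Former etrasimod | Total, mean weeks |
|---|---|---|---|
| Week 25 | 1 | 25 | 17.6 |
| Week 28 | 4 | 28 | 20.6 |
| Week 36 | 12 | 36 | 28.6 |
| Week 44 | 20 | 44 | 36.6 |
| Week 52 | 28 | 52 | 44.6 |

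The 24-week gap is present at every OLE visit.

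**Size on the outcome scale (illustration only).** The documents give no expected Week 24 change for this purpose. If former etrasimod subjects had a mean Week 24 change of g points, the Total column would carry 54/78 × g points accrued before the extension: 3.5 for g = 5, 6.9 for g = 10 and 13.8 for g = 20.

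**After the change.** With a Week 24 pre-dose baseline for all, change from OLE Baseline at Week 52 covers 28 weeks in every subject, and the share without a within-OLE change falls from 69.2% to zero. The DB Baseline summaries are unaltered.

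**The case against.** The best defence is that the SAP choice amounts to a last-value-before-first-etrasimod baseline. That shows total effect since the drug was started and suits an objective framed as long-term safety and efficacy up to 52 weeks. No stated objective asks for change after Week 24. The choice is also declared in Table 4, so nothing is hidden. This stands as an argument that the quantity is legitimate. It does not justify the name or the pooling: by double-blind arm, the same quantity is already readable as the DB Baseline change for the etrasimod arms and the Week 24 change for placebo. Nor is it a clarification, because the protocol rule was already clear and is reversed for most subjects.

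A second defence is that the information can be recovered. Change from DB Baseline appears in the same columns on a single time origin, observed values by visit are planned for laboratory, lung and eye measures, and the mean within-OLE shift in an etrasimod arm can be approximated by subtracting the Week 24 mean. This is partly right. But the Week 24 double-blind tables include subjects who never enter the OLE, and subtracting means gives no SD of the paired change.

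Several stronger readings are tempting, and the documents do not support them:

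- That the SAP removes an efficacy summary the protocol had promised. The protocol commits to both baselines for safety only; the SAP itself extended this to efficacy.
- That all OLE columns are mixed. The three double-blind-arm columns are not; for the 2 mg and 3 mg arms they are merely redundant.
- That nothing uses Week 24 as reference for former etrasimod subjects. Acute post-dose vital-sign and ECG changes at Week 24 are taken from that visit's pre-dose value (SAP 11.3, 11.5).
- That the lung and eye criteria are distorted. The criteria for decline in FEV1, FVC and DLCO and for increase in foveal thickness use DB baseline for everyone (SAP 11.6, 11.7).

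Finally, table layouts sit in a separate document, so the pooling is read from the column definitions in SAP Appendix 1.

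**Conclusion.** The point holds in limited form. SAP 4.1 departs from Protocol 11.10. As a result, one of the two planned OLE change summaries is redundant for the double-blind etrasimod arms, and the OLE dose-path and Total columns combine changes with starting points 24 weeks apart. The 69% is a share of planned randomized subjects; under the assumptions shown it stays between about 64% and 74%. It should not be quoted as a share of the OLE sets. The contrast of 28 with 52 weeks belongs to the Week 52 visit alone. The size of any distortion in SALT I or safety means is unknown, because it depends on the Week 24 response.

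The consequence is small. The OLE analyses are descriptive, with no testing, and no primary or secondary double-blind result changes. What is lost is a directly tabulated paired change after Week 24, including after the step from 2 mg to 3 mg.

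**What to change.** In SAP 4.1 and Table 4, restore the last value before the first OLE dose at Week 24 as OLE Baseline for all subjects, for the change summaries in 10.5 and 11.8. Keep the DB Baseline summaries as planned. SAP Table 1, which already places OLE Baseline at OLE Day 1, would then fit every subject.

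If a last-value-before-first-etrasimod baseline is still wanted, give it its own name and present it by double-blind arm only, not in the OLE dose-path or Total columns.

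The cost is SAP wording and one baseline flag in the OLE programs, plus at most one extra set of descriptive columns if the additional baseline is shown. No information is given up.
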